### **Laboratory Test Abnormalities**

For laboratory test abnormalities that meet the definition of an SAE, that required the subject to have the investigational product discontinued or interrupted or required the subject to receive specific corrective therapy, the clinical diagnosis rather than the laboratory term will be used by the reporting investigator (e.g., anemia versus low hemoglobin value).

### **Life-Threatening**

Life-threatening refers to any adverse event that places the patient at immediate risk of death from the reaction as it occurred. It does not include a reaction that, had it occurred in a more severe form, might have caused death. (Source CFR: 21 CFR 312.32)

### **Requires or Prolongs Hospitalization**

A patient must be admitted to the hospital for a period greater than 24 hours, for the hospitalization to be considered a serious adverse event. Elective hospital admissions, scheduled prior to the study, are not considered serious adverse events unless the hospitalization is prolonged. Planned admissions (as part of a study), hospitalizations for less than 24 hours, hospitalization for an elective procedure, and Emergency Room/Department visits are not considered serious adverse events. Exception: Any disposition of the patient to the hospital or emergency room within 24 hours following study drug (infusion) therapy.

## **7.4 Reporting Procedures**

The SAE reporting flow chart will be included in the MOP.

### **Protocol Specific Exceptions to SAE Reporting**

Specified outcome events in the study will be recorded in their respective appropriate modules of the eCRF. These events and specific corresponding symptoms will NOT require reporting as serious adverse events on the SAE eCRF. Specifically, the events covered in this exception are as follows:

1. Myocardial infarction
2. Stroke
3. Coronary revascularization
4. Hospitalization for unstable angina

### **Serious Adverse Event Reporting**

The site investigator is responsible for monitoring the safety of participants enrolled into the study. All SAEs must be reported from the time of randomization through 30 days post final infusion, using the electronic data capture system. Non-serious adverse events will not be collected on the eCRF. All SAEs whether or not deemed drug-related or expected must be reported by the investigator or qualified designee within 24 hours of first becoming aware of the event. The investigator or qualified designee will enter the required information regarding the SAE into the appropriate module of the eCRF. If the eCRF system is temporarily unavailable, the event, including the investigator-determined causality to study drug will be reported via the back-up paper SAE form to DCRI Safety Surveillance at [name]. Upon return of the availability of EDC system, the SAE information must be entered into the eCRF.

Adverse events that are serious and drug (infusion) therapy related or result in death will be reviewed by the DCRI Safety Surveillance Department Medical Monitor to assess medical clarity and unexpectedness. DCRI Safety Surveillance will review all SAE data including all deaths, within 1-2 business days to:

1. Ascertain seriousness
2. Ascertain drug (infusion) therapy causal relationship
3. Verify that all data are complete
4. Follow-up with the site for incomplete data and/or data clarification.

This will include, but will not be limited to, ensuring that serious criteria have been met and the SAE data received are reviewed, entered and coded using the MedDRA coding dictionary.

DCRI Safety Surveillance will notify the study sponsors (NIH and TACT2 Principal Investigators from Mount Sinai and Duke Clinical Research Institute), and Data Safety Monitoring Board Chairman (DSMB) in a blinded fashion, within 1 business day of receipt of the initial notification of the SAE, of:

- All serious adverse events that are drug (infusion) therapy related – defined as taking place within 24 hours of an infusion, and attributed to the infusion by the site PI or by DCRI Medical Monitor, and/or
- All SAEs resulting in death

The DCRI Safety Surveillance will provide the DCRI Regulatory Services with the event specific forms necessary to report the expedited adverse event according to country specific regulatory guidelines. This will include all deaths assessed by the DCRI Medical Monitor as warranting expedited reporting to the regulatory authorities and all adverse events that are serious, unexpected and drug (infusion) therapy related (as assessed by the site investigator, DCRI Medical Monitor and TACT2 study leadership).

### **Procedures for Enhanced Reporting of Specific Adverse Events**

DCRI Safety Surveillance will also report specific adverse and/or serious adverse events, not otherwise eligible for expedited SAE reporting as in Section 7.2, within 2 business days to the DSMB or its designee, and the NIH Program Officers. The adverse events for enhanced scrutiny include:

1. Heart failure hospitalization during the entire infusion phase of the patient's participation in the study, not otherwise subjected to expedited SAE reporting.
2. Any disposition of the patient to the hospital or emergency room within 24 hours following study drug (infusion) therapy, not otherwise subject to expedited SAE reporting.

These events would not be eligible for expedited SAE reporting if the causality criterion were not met. Notification of these events will be made electronically.

### **7.5 Follow-up for Serious Adverse Events**

All reported SAEs will be followed until resolution, stabilization or until 60 days after the last patient enrolled in the trial completes the study drug (infusion) therapy. At the time of database lock, unresolved SAEs may be closed (final outcome assigned as "unresolved") per the discretion of the DCRI Medical Monitor and/or the DCC PI. The site investigator will be responsible for reporting adverse events and unanticipated problems involving risks to subjects to their local IRBs/IECs in accordance with local regulations.

### **7.6 Safety Monitoring**

#### **Data and Safety Monitoring Board**

TACT2 will have an independent DSMB appointed by and reporting to NIH. The DSMB will be expected to meet with the study leadership at least 2 times per year to review study progress and overall safety. For ethical reasons, an interim examination of key safety and endpoint data will be performed during the course of the trial. A separate DSMB charter outlining the operating guidelines for the committee and the protocol for evaluation of data will be created prior to study enrollment and agreed upon during the initial meeting of the DSMB.

## **8. INTERVENTION INTERRUPTION**

### **Reasons for Withdrawal/ Interruption**

There may be reasons for subject withdrawal and/or interruption of the study infusions and/or OMVM.

Some possible reasons are:

- Died
- Lost to follow-up
- Informed consent withdrawal

Subject adherence and retention strategies will be included in the site personnel training. Site personnel will be encouraged to have weekly communications with enrolled subjects as a means of continued participation. The site investigator should make every attempt to accommodate the subject to continue the therapy where feasible and encourage subject to allow follow-up by the DCRI Call Center.

### **Withdrawal Procedures**

Site study personnel must immediately communicate, with the CCC PI, all information from subjects that express desire to stop study treatment (either infusions or OMVM), follow-up or withdrawing informed consent. When all attempts by the site study personnel to accommodate the subject are unsuccessful, the final disposition of a subject withdrawal from study treatment and/or follow-up will **require** approval by the CCC PI. See the MOP for details.

## **9. STATISTICAL CONSIDERATIONS**

### **9.1 General Design Issues**

Analysis of the TACT2 2x2 factorial trial will be based on intention to treat (ITT). That is, participants will be analyzed (and endpoints attributed) according to the treatment strategy to which participants are randomized, regardless of subsequent additional post-randomization treatment and medical care. Statistical comparisons will be performed using two-sided significance tests. Treatment dropouts and consent withdrawals will be tracked by verifiable means within the eCRF at each follow-up interval. Baseline demographic and clinical variables will be summarized for each randomized arm of the study. Descriptive summaries of the distribution of continuous variables will be presented in terms of percentiles (e.g., median, 25th and 75th percentiles) along with means and standard deviations. Categorical variables will be summarized in terms of frequencies and percentages.

### **9.2 Sample Size and Randomization**

Participants will be randomized in a 1:1:1:1 allocation ratio using simple randomization. The study was originally designed to enroll a total of 1200 participants with a minimum follow-up of 12 months. The DSMB conducted a blinded review of enrollment aggregate event rates, and projected event rates in July 2019. Following this blinded review, the

DSMB recommended a reduction in the target sample size to 1100 participants and an increase in the minimum follow-up from 1 year to approximately 2.5 years. Due to slowed enrollment related to the COVID-19 pandemic, in the fall of 2020, the DSMB and the NIH leadership agreed to a proposal to complete enrollment by 12/31/2020 with an allowance to follow the study participants until there are enough primary endpoint events to maintain 85+% power.

Several design factors and research objectives have been considered in developing an appropriate sample size for the TACT2 study. First, patient enrollment and follow-up has been determined so there would be a sufficient number of endpoints to provide a high degree of confidence for testing the primary hypothesis. Second, the statistical power for secondary endpoints has been considered. Finally, the sample size has been determined to provide a reasonable level of confidence for detecting clinically important differences in outcome between treatment strategies even if current projections of event rates and hypothesized differences in clinical outcomes between the treatment groups prove to be optimistic.

Table 3 shows the required number of endpoint events to have 80% to 90% power with hazard ratios varying from 0.50 to 0.75. The two factors (EDTA chelation and OMVM) are assumed to be additive for the sample size calculations. Based on TACT we anticipate a hazard ratio of 0.70 (active chelation vs. placebo chelation) to determine the sample size requirements. This hazard ratio assumption is very conservative compared to the observed effect in TACT. Assuming a two-sided 0.05 type I error rate and approximately 5% consent withdrawal or loss-to-follow-up per year, the final sample size of 1000 participants will provide approximately 85% power to detect a hazard ratio of 0.70 for the primary endpoint of time to all-cause mortality, myocardial infarction, stroke, coronary revascularization, or hospitalization for unstable angina comparing active chelation vs. placebo chelation.

Table 3. Required number of events						
	HR=0.50	HR=0.55	HR=0.60	HR=0.65	HR=0.70	HR=0.75
80% power	65	88	120	169	247	379
85% power	75	100	138	194	282	434
90% power	87	118	161	226	330	508

Calculations performed using nQuery 7.0 and assume a 0.05 type I error rate (two-sided) with 1:1 randomization.

For other exploratory endpoints, we outline a general power justification for comparisons to be made among the four arms of the 2x2 factorial design. We anticipate that roughly 1000 participants will have blood and urine samples available from baseline and one or more follow-up time points. A sample size of 250 participants per group will provide 80% or greater power for any between group differences greater than  $\frac{1}{4}$  of a standard deviation. These calculations are based on a two-sample t-test and assume a two-sided type I error rate of 0.05.

### **9.3 Definition of ITT Population**

The ITT population will correspond to all randomized participants. The primary and secondary analyses will follow the ITT principle.

### **9.4 Interim Analyses and Stopping Rules**

For ethical reasons, interim examinations of key safety and process data will be performed at regular intervals during the course of the trial. It is anticipated that the DSMB will meet at 6-month intervals to review the accumulating data. Prior to performing interim analyses, aggregate event rates will be assessed to compare predicted vs. actual event rates. The DCC will create regular reports to track patient enrollment reports, rates of adherence with the assigned treatment strategy, and frequency of protocol violations. Prior to each meeting, the data coordinating center will conduct any requested statistical analyses and prepare a summary report along with the following information: patient enrollment reports, rates of adherence with the assigned treatment, and description of SAEs (statistical comparisons of the randomized arms with respect to these SAEs will use chi-square or other appropriate 2-sample or >2-sample methods). Safety data will be reported by all 4 treatment groups as well as active chelation vs. placebo chelation and active OMVM vs. placebo OMVM. The DSMB will review data partially masked by study group (such as X vs. Y and not active chelation vs. placebo chelation).

Safety reports will be prepared for the DSMB approximately once every 3 months. Futility and efficacy monitoring will focus solely on the active chelation vs. placebo chelation comparison. The DSMB will review the active OMVM vs. placebo OMVM data for safety purposes only.

For futility monitoring, TACT2 will employ a modification of the inefficacy monitoring guideline of Freidlin, Korn, and Gray to stop the trial if the chelation strategy is not beneficial. We plan to use a conservative boundary, denoted as LIB0, along with a harm look at 25% of expected information. This approach will include 4 interim looks scheduled at roughly 25%, 40%, 60%, and 80% of expected information. With the proposed design, a total of roughly 280 primary endpoint events are expected and the first interim review for futility and efficacy will be scheduled after approximately 70 primary endpoint events have been observed. The harm look at 25% of expected information would suggest stopping the trial if the data suggests harm for the chelation strategy vs. the placebo chelation with p-values <0.05 for both the primary outcome and the all-cause mortality endpoint. For the interim reviews at 40%, 60%, and 80%, the inefficacy guideline suggests stopping the trial if the chelation infusion strategy has a hazard ratio > 1.0 compared to placebo for both the primary outcome and the all-cause mortality endpoint. This inefficacy monitoring approach will result in a trivial loss of power and requires no sample size adjustment.

The method of Haybittle and Peto will be proposed as the primary guide for interpreting interim efficacy analyses. The timing of the interim efficacy analyses will correspond to the futility monitoring reviews (i.e. at roughly 25%, 40%, 60%, and 80% of expected information). The proposed efficacy monitoring guideline requires large critical

values ( $Z=3$ ,  $p\leq 0.001$ ) for every assessment until the planned final analysis. The TACT2 investigators suggest that both the primary outcome and the all-cause mortality outcome are evaluated at the interim reviews with a focus on the comparison of active chelation vs. placebo.

The CCC PI, DCC PIs, CCC staff, clinical study Co-PIs, site investigators, NIH Program Staff and study participants will remain blinded until database lock. Limited staff will be unblinded to handle randomization codes, deliver the interventions to sites, and prepare DSMB reports. The statistical staff responsible for preparing DSMB reports will not directly interact with the clinical team that delivers care to the study participants or the CEC that determines clinical events.

## **9.5 Outcomes**

### **9.5.1 Primary Outcome**

The primary outcome is the time to the first occurrence of all-cause mortality, myocardial infarction, stroke, coronary revascularization, or hospitalization for unstable angina.

### **9.5.2 Secondary Outcomes**

The three secondary outcomes of TACT2 are:

- the overall rate of events due to all-cause mortality, myocardial infarction, stroke, coronary revascularization, or hospitalization for unstable angina events
- the time to the first occurrence of cardiovascular mortality, recurrent myocardial infarction, or stroke
- the time to all-cause mortality

The TACT2 CEC will review all primary and secondary endpoints.

## **9.6 Data Analyses**

### **Primary Endpoint Analysis**

The primary objective of TACT2 is to determine if the chelation-based strategy increases the time to composite of all-cause mortality, myocardial infarction, stroke, coronary revascularization, or hospitalization for unstable angina compared to the placebo chelation strategy. The statistical comparison will be based on the time from randomization to the first occurrence of all-cause mortality, myocardial infarction, stroke, coronary revascularization, or hospitalization for unstable angina. The Cox proportional hazards regression model will be used to assess outcome differences between the treatments. An initial Cox model will include indicator variables for the active chelation and active OMVM groups, an interaction term for the active chelation and active OMVM, age, sex, and use of insulin. If the interaction term for the active chelation and active OMVM is not statistically significant at the two-sided 0.05 level, the primary analysis will be based on a Cox model which includes indicator variables for the active chelation and

active OMVM groups, age, sex, and use of insulin. The chelation treatment effect will be summarized using hazard ratios and associated 95% confidence intervals. In addition to the statistical hypothesis testing, Kaplan-Meier survival estimates will be constructed based on the time from randomization to the first primary event occurrence.

The OMVM treatment effect from the Cox model will be estimated using the Cox model described above. Given the results of TACT and the focus on chelation therapy, the interpretation of the OMVM treatment effect will be considered exploratory.

Assessment of the proportional hazards assumption will be evaluated using visual analysis (of the survival and log {-log (survival)} functions), as well as tools within the “proportionality test” statement of Proc Phreg in SAS.

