## **Screening assessment, enrollment, and randomization**

### **Screening Visit**

After providing informed consent, the site will enter the patient in the EDC system where a unique identifier will be assigned. The patient will have the medical history reviewed by study staff, and blood and urine samples will be drawn. Eligibility will be based on the following:

- All inclusion criteria are met
- No exclusion criterion is present

Data collected will include relevant cardiac history, particularly of the qualifying MI (anterior or non-anterior), whether patients have Type 1 or Type 2 diabetes, complications of diabetes, and treatment of diabetes. Sites are encouraged to discuss any questions about qualifying criteria with the CCC. Medication data will include post-MI evidence-based medications and treatments for diabetes. Laboratory test results will be entered to characterize the patient population, in particular with regards to diabetes control, renal function, and safety parameters to be followed during follow-up.

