1.1 Study Design

The Trial to Assess Chelation Therapy 2 (TACT2) is a randomized, double blinded, placebo-controlled 2x2 factorial clinical trial. The study treatments are edetate disodium-based chelation (weekly infusion for 40 weeks) and high-dose oral multivitamins and multi-minerals (OMVM) (twice daily for up to 5 years). Subjects with diabetes mellitus with a prior myocardial infarction (MI) are recruited from participating sites in the US and Canada and randomized in a 1:1:1:1 fashion to 4 groups:

- i. Active chelation + active OMVM
- ii. Active chelation + placebo OMVM
- iii. Placebo chelation + active OMVM
- iv. Placebo chelation + placebo OMVM.

Patients will be followed for clinical events until the earlier of database lock or five years from randomization. Clinical outcomes will be collected by study sites at each infusion visit and by the DCRI Call Center at month 6 and 12, and every 4 months afterwards with the last assessment at month 60.

TACT2 is an event driven trial with a plan to continue until at least 282 primary endpoint events are identified. The original planned sample size was 1200 participants. The sample size was later modified to 1100. The final enrollment is 1000, but with an increased follow-up time to preserve statistical power. More details on sample size and power calculation are included later in the SAP.

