3.2.1 Primary Analysis

The primary objective is to determine if the chelation-based strategy increases the time to composite endpoint compared with the placebo chelation strategy. The primary composite endpoint will be analyzed using a Cox proportional hazards regression model of time from randomization to the first occurrence of all-cause mortality, MI, stroke, coronary revascularization, or hospitalization for unstable angina.

The primary analysis will be based on a Cox model which includes indicator variables for the active chelation as the primary variable of interest and active OMVM groups, age, sex, and baseline insulin use as covariates. Age will be included in the model in the form of cubic splines using three knots at 10th, 50th, and 90th percentiles. Two separate manuscripts will explore the effect of active OMVM and the effects of chelation by OMVM.

The chelation treatment effect will be summarized using hazard ratios and associated 95% CIs. A hazard ratio of < 1 would suggest a benefit for the chelation-based therapy. Kaplan Meier survival estimates will be constructed based on the time from randomization to the first

primary event occurrence. Events occurring after withdrawal of consent or informed consent expiration will be censored.

The OMVM treatment effect from the Cox model will be estimated using the Cox model described above. A hazard ratio of < 1 would suggest a benefit for OMVM treatment. Given the focus on chelation therapy, the interpretation of the OMVM treatment effect will be considered exploratory. A full set of analyses of the 2x2 design will be reported in a separate manuscript.

Four interim analyses were conducted at 25%, 40%, 60%, and 80% of expected information using a Haybittle-Peto-type boundary for efficacy (i.e. $p \leq 0.001$, $Z=3$). For this reason, the adjusted two-sided significance level for the final analysis is 0.05 (i.e., the corresponding critical value, $Z = -1.96$).

Formal statistical hypothesis testing will follow a hierarchy based on statistical significance of the prior endpoint. If the prior endpoint is statistically significant at the 0.05 level, the next endpoint's p-value will be tested for significance. The outcome hierarchy will be evaluated as follows:

- 1) Primary composite outcome
- 2) Secondary all-cause mortality outcome (with conservative censoring)
- 3) Secondary composite outcome of cardiovascular mortality, MI, or stroke

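### Optional efficiency gain, not an error: four baseline prognostic factors could be added to the primary Cox model at little cost, for about 0 to 3 points of power if they are weak to moderate predictors

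*Protocol*

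**What the plan says.** Protocol 9.6 bases the primary analysis, once a chelation-by-OMVM interaction has been tested and found non-significant, on a Cox model with indicators for active chelation and "active OMVM groups, age, sex, and use of insulin". SAP 3.2.1 has chelation as the variable of interest, with "active OMVM groups, age, sex, and baseline insulin use as covariates", and models age as a three-knot spline. Neither document explains the choice of covariates.

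Four other candidates are available at baseline:

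- **Renal function and HbA1c.** Both are screening laboratory tests (Protocol 6.1) and both decide eligibility (Protocol 4.1). On screening, Protocol 6.2.1 says: "Laboratory test results will be entered to characterize the patient population, in particular with regards to diabetes control, renal function". Creatinine clearance is computed for dosing (Protocol 5.1).
- **MI location.** Anterior versus non-anterior is recorded for the qualifying MI at screening (Protocol 6.2.1).
- **Known peripheral artery disease at baseline.** It is a pre-specified subgroup in Protocol 9.6 and SAP 3.4, as is MI location.

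On allocation, Protocol 9.2 states: "Participants will be randomized in a 1:1:1:1 allocation ratio using simple randomization". None of the sensitivity analyses in SAP Table 3 or SAP 3.2.2 uses a fuller covariate set.

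**The concern.** In a Cox model, leaving out baseline variables that predict the outcome pulls the estimated treatment hazard ratio toward 1 and lowers power, even when the arms are balanced. Four extra variables are a light load for a model fitted to about 282 events.

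The primary test also gates the rest. Under the hierarchy in SAP 3.2.1, a non-significant primary result stops formal testing of all three secondary endpoints. If a chance imbalance in, say, renal function appeared after unblinding, no pre-specified analysis would address it, and any correction would be post hoc.

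**Working it through.** **Inputs from the documents.** Protocol 9.2: "Assuming a two-sided 0.05 type I error rate and approximately 5% consent withdrawal or loss-to-follow-up per year", and "the final sample size of 1000 participants will provide approximately 85% power to detect a hazard ratio of 0.70". SAP 1.1: "plan to continue until at least 282 primary endpoint events are identified". Note to Protocol Table 3: "Calculations performed using nQuery 7.0 and assume a 0.05 type I error rate (two-sided) with 1:1 randomization".

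**Step 1: reproduce the plan's figure, without covariates.** The Schoenfeld formula for 1:1 allocation is

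events = 4 × (z₀.₉₇₅ + z₀.₈₅)² / (ln HR)² = 4 × (1.960 + 1.036)² / (0.3567)² = 35.91 / 0.1272 ≈ 282.3.

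The protocol states 282. In reverse, z = (√282 / 2) × 0.3567 − 1.960 = 1.035, which is 84.96% power. The planned power therefore does not rely on any covariate adjustment.

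**Step 2: simulate the planned and extended models at a fixed 282 events.** Set-up: 1,000 participants; simple 1:1 allocation to chelation and to OMVM; true conditional HR 0.70; exponential event times; administrative follow-up of 2.5 to 5 years, scaled to give exactly 282 events. Age, sex and insulin are represented by one score with a log-hazard SD of 0.3. The four added covariates are independent and normal. There were 6,000 replicates per setting, with both models fitted to each.

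The prognostic strengths are assumptions. With k the HR per SD of each covariate, the combined log-hazard SD of the four is √4 × ln k = 2 ln k.

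| HR per SD, each | Combined SD | Mean HR, planned → extended | Power, planned | Power, extended | Gain in points (simulation SE) |
|---|---|---|---|---|---|
| 1.1 | 0.19 | 0.700 → 0.698 | 84.9% | 85.1% | 0.3 (0.2) |
| 1.2 | 0.36 | 0.704 → 0.698 | 83.3% | 84.9% | 1.6 (0.3) |
| 1.3 | 0.52 | 0.711 → 0.698 | 81.3% | 84.6% | 3.4 (0.3) |
| 1.5 | 0.81 | 0.727 → 0.698 | 75.0% | 84.2% | 9.2 (0.5) |

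Gains were computed before the power figures were rounded.

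**Step 3: where the gain comes from.** It comes from less attenuation, not from a smaller standard error. At 1.3 per SD, the SE of the log HR rises slightly, from 0.1207 to 0.1212, while the HR moves from 0.711 to 0.698.

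**Step 4: downside checks.** With null covariates, power is 83.8% versus 83.7% (2,000 replicates). With a true HR of 1, both models reject in 5.2% to 5.8% of trials.

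**Step 5: scale.** At 1.3 per SD, going from 81.3% to 84.6% power is equivalent to ((1.96 + 1.02) / (1.96 + 0.89))² ≈ 1.09 times the information, or about 26 events on 282.

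**The case against.** The strongest reply is that nothing here is wrong. The covariate list is short, pre-specified and the same in both documents, and omission works against the treatment effect without inflating type I error. All of that stands.

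A reader might go further and infer one of three stronger claims, which the documents do not support:

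- **That the trial is short of power because of the omission.** The 85% figure reproduces without covariates. If 0.70 is read as the hazard ratio that the planned model targets, adjustment adds margin above 85% and repairs no deficit. SAP Table 2 projects 87% to 89% power with 288 to 299 events. Appendix I's minimum scenario is lower, at 76% to 78% with 235 to 244 events, but that comes from the event rate.
- **That the loss is large.** Part of the fall seen in a simulation that fixes the placebo rate (10.4 per 100 patient-years) is due to fewer events. As the combined SD goes from 0 to 0.7, events drop from 299 to 274 and power with adjustment itself falls from 88.1% to 82.3%; without adjustment it is 76.3%. The SAP plans for at least 282 events, so the fixed-event comparison is the relevant one.
- **That simple randomization leaves these factors unbalanced.** It balances them in expectation. With about 500 per chelation arm, the SE of a standardized baseline difference is √(1/500 + 1/500) ≈ 0.06 SD. Only chance imbalance remains.

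The practical objections also stand. The missing-covariate rule in SAP 2.6 names only age, sex and insulin and imputes the mode, which does not suit continuous variables. Inclusion criterion 3b admits participants whose MI hospitalization records are unavailable, so MI location may be uncertain for some. The recurrent-event models in SAP 3.3.1 have their own covariate list. Because the hazard ratio is non-collapsible, the conditional value being estimated would shift slightly. These points shape the change but do not remove the benefit.

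**Conclusion.** A worthwhile, low-cost improvement to a valid plan. At 282 events the gain is 0.3 to 3.4 percentage points for weak to moderate covariates (HR per SD 1.1 to 1.3) and 9.2 points only if each is strong (1.5). There is essentially no loss if they carry no information.

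The size rests on prognostic strengths that the documents do not give and on independence among the covariates. Three features point to the lower end. Creatinine clearance is calculated partly from age and sex, which are already in the model. Correlation with insulin use is plausible, particularly for HbA1c. The exclusions for creatinine above 2.0 mg/dL and HbA1c above 11% narrow two of the ranges. The simulation also had no dropout beyond administrative censoring.

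**What to change.** Before unblinding:

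1. In SAP 3.2.1, add baseline creatinine clearance, baseline HbA1c, known peripheral artery disease and MI location to the pre-specified Cox model. State the functional form for the two continuous variables, as is already done for age.
2. Make the same addition to the separate covariate list in SAP 3.3.1. The time-to-event secondary endpoints in SAP 3.3.2 follow the primary analysis by cross-reference (it cites a Section 4.1, but the analysis is in 3.2.1).
3. Extend SAP 2.6 with a missing-data rule suited to continuous covariates, not the mode, and add a category for unknown MI location.
4. Keep the age, sex and insulin model as a sensitivity analysis, so that both hazard ratios are reported.

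If the primary model is to stay as it is, the extended model could instead be pre-specified as a sensitivity analysis. That covers chance imbalance but gives no power gain for the primary test.

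The cost is a few degrees of freedom, a short additional missing-data rule, and a conditional hazard ratio slightly different in value from the one now planned. No new data collection is needed.
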